3.7.2 Muscle Thickness

Muscle thickness was assessed via ultrasonography (HD11 XE, Philips, Netherlands) using a linear-array transducer with 3-12 MHz (L 12-3, Philips, Netherlands) and was used as an index of muscle hypertrophy for the quadriceps musculature. This technique has been previously employed to measure the hypertrophic response to RET (182) and has compared favorably to magnetic resonance imaging for muscle size (288). Ultrasound scans took place during pre-, mid-, and post-testing time points in the supine position after participants had been resting for 10 minutes to allow for any fluid shift to occur. During this time, specific anatomical locations were identified and marked with a water-soluble pen at 50% of distance between the greater trochanter and the lateral condyle of the femur and 50% of the distance between the anterior superior iliac spine and the superior border of the patella. These anatomical locations allowed for imaging of the vastus lateralis, vastus intermedius, and rectus femoris muscles (1, 146).

All ultrasound scans were completed by the same person and conducted on the right side of the body. Prior to each scan, a water-soluble transmission gel was applied to the transducer for optimal acoustic contact. Furthermore, minimal pressure was applied to the transducer to limit compression of tissues. Muscle thickness was measured as the distance (cm) from the adipose-muscle interface to the muscle-fascicle or muscle-bone interface. The values from the three sites were summed together for a total muscle thickness measure. Muscle thickness test-rest reliability measured by intraclass correlation coefficients (model 3,1) for the muscle groups were: vastus lateralis, 0.977 (95% confidence intervals: 0.835, 0.997); rectus femoris 0.995 (95% confidence intervals: 0.957, 0.999); vastus intermedius 0.977 (95% confidence intervals: 0.834, 0.998).

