3.5 Protein Supplementation

Protein and placebo supplementation were provided in a double-blind, placebo-controlled manner throughout the 12-week intervention. Participants were randomly assigned (<https://www.randomizer.org>) to 1 of 3 groups: 1) Post-ex consumed a protein supplement immediately post-exercise and a non-caloric placebo 30 minutes before sleep, 2) Pre-sleep consumed a non-caloric placebo immediately post-exercise and the protein supplement 30 minutes prior to sleep, or 3) Ex only did not consume protein or placebo supplementation. Participants were instructed to fast for at least 2 hours prior to each exercise session and for 2 hours post exercise (9), except for the consumption of the protein or placebo supplement, along with a 190-kcal snack bar (Nature Valley™, Oats 'N Honey, General Mills, MN), to reduce the timing effects of normal meals on exercise adaptations. Additional instructions were given to consume the nighttime pre-sleep protein or placebo supplement at least 2 hours after their last feeding (e.g. meal or snack) and approximately 30 minutes before sleep with no other food. On non-exercise days, participants were instructed to consume the protein or placebo supplement in between their normal breakfast and lunch.

To ensure a double-blind, placebo-controlled design, an assistant not associated with outcome measures created containers of protein and placebo supplements in advance and did not reveal the identity until the conclusion of the study. Participants were provided two containers with approximately 25 servings (3.5 weeks of supplements) of protein and placebo

supplementations. Each serving was weighed on a digital scale (Etekcity Co., Anaheim, CA) and placed within individual sealable bags (Ziploc; SC Johnson Co., Racine, WI) to ensure accurate servings. Furthermore, both supplements were masked for flavor, and texture. Lastly, participants were instructed to mix their supplement only with water.

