3.8 Sample Size Justification and Statistical Analysis

An a priori analysis was conducted with an effect size F of 0.25 calculated using mean and standard deviations from previously reported changes in LBM in older men (350) with power set to 0.8 and α set to 0.05 for 3 groups and 3 measurements. With an expected dropout rate of 15% (110), a sample size of 36 was adequate and provided an even distribution between groups.

A one-way analysis of variance (ANOVA) was used to analyze baseline differences and total training volume among groups. A 3x2 mixed model ANOVA with group as the between subjects' factor (Post-ex, Pre-sleep, Ex only) and time as the within-subjects factor (pre and post) was performed on all dependent variables except for muscle thickness, 1-RM strength, muscle power, and appetite, where a 3x3 mixed model ANOVA (Post-ex, Pre-sleep, Ex only x pre, mid, post) was used. Pearson product-moment correlation, or Spearman's correlation in the event of normality violation, was used to determine the relationship between changes in free IGF-1 and changes in body composition, muscle thickness, 1-RM strength, muscular power, and cognitive assessments.

Outliers were removed and defined as values outside of the mean \pm 3 standard deviations. Data were tested for normality (Shapiro-Wilk), homogeneity of variances (Levene's test), and sphericity (Mauchly's test) where appropriate. When normality or homogeneity of variances was violated, non-parametric testing or data transformation was performed. For a mixed model ANOVA, if transformation could not correct the violation, original data were analyzed, as there are no non-parametric alternatives. When sphericity was violated, the main time and group x time interactions were interpreted with the Greenhouse-Geisser estimation.

Significance was set at $p \leq 0.05$. Trends were noted for p -values between 0.051-0.10. For significant interactions and main effects, pairwise comparisons with Bonferroni adjustments were conducted (296, 332). Pearson correlation coefficients (r) or Spearman's correlation coefficients (r_s) were interpreted as "negligible" = < 0.30 , "low" = $0.30-0.50$, "moderate" = $0.50-0.70$, "high" = $0.70-0.90$, and "very high" = > 0.90 (244). Percentage change was calculated as $((\text{post value} - \text{pre value}) * 100)$. All analyses were performed with SPSS version 25

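### Muscle thickness is read with no stated masking to visit or to Ex only membership, so reader drift could appear as growth over time

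*Combined protocol and SAP*

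**What the plan says.** Section 3.7.2 uses ultrasound muscle thickness as the index of quadriceps hypertrophy, scanned at pre, mid and post. On the operator it says: "All ultrasound scans were completed by the same person and conducted on the right side of the body". On the measurement it says: "Muscle thickness was measured as the distance (cm) from the adipose-muscle interface to the muscle-fascicle or muscle-bone interface". The three site values are summed. The section also covers rest before scanning, landmarks, water-soluble skin marks, gel and probe pressure ("minimal pressure was applied to the transducer to limit compression of tissues"), and it reports test-retest ICCs (model 3,1) of 0.977, 0.995 and 0.977. It does not say who placed the measurement borders, whether images were stored or coded, or whether the reader knew the visit.

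Section 3.5 describes the masking: "Protein and placebo supplementation were provided in a double-blind, placebo-controlled manner throughout the 12-week intervention". To achieve this, "an assistant not associated with outcome measures created containers of protein and placebo supplements in advance" and kept the code until the study ended. Both supplement arms took a protein and a placebo serving. The third arm is different: "Ex only did not consume protein or placebo supplementation".

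Section 3.8 gives the analysis of thickness: "a 3x3 mixed model ANOVA (Post-ex, Pre-sleep, Ex only x pre, mid, post) was used". Bonferroni pairwise comparisons follow significant main effects as well as significant interactions.

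**The concern.** Placing a border on an ultrasound image involves judgement. A reader who knows that an image comes from week 12 of a training programme may expect growth and place the border slightly deeper. A small shift in the same direction at each of three sites adds up in the sum.

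The time effect is a stated target. Section 3.1 says that the three assessments were made to describe the time course of muscular adaptation. All three arms trained, so no untrained arm could reveal drift. The reported ICCs do not settle the matter: in its usual consistency form, ICC(3,1) ignores a constant difference between sessions. High precision even makes a small constant shift easier to declare significant.

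Membership of Ex only is a second route. Those men took nothing, so the placebo cannot conceal their arm, and the plan does not say that the scanner or reader was kept unaware of it. A shift that differs between Ex only and the supplement arms would enter the group comparison itself.

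**Working it through.** **1. What the masking covers**

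| What the reader could know | Covered by section 3.5? |
|---|---|
| Post-ex or Pre-sleep | Yes, both take two products and the code is held elsewhere |
| Ex only or a supplement arm | No, Ex only takes neither product |
| Pre, mid or post visit | No, product masking has no bearing on visit |

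**2. Inputs.** From the documents: n = 30, split 9/11/10 (section 3.3), α = 0.05 (section 3.8), and the ICCs (section 3.7.2). The documents give no SD of change in thickness and no size of reader shift. Assumed: SD of change in summed thickness 3 mm (range 2 to 4); shift 0.3 or 0.5 mm per site in the same direction, so 3 × 0.3 = 0.9 mm or 3 × 0.5 = 1.5 mm summed; no true change. The plan has no figure of its own on this point to reproduce.

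**3. Shift common to all arms: time effect.** Two-sided paired t-test, pre to post, 29 df, critical value 2.045, noncentrality = (shift/SD) × √30. For 0.9 mm and SD 3 mm this is 0.30 × 5.477 = 1.643.

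| Summed shift | SD 2 mm | SD 3 mm | SD 4 mm |
|---|---|---|---|
| 0.9 mm | 66% | 36% | 22% |
| 1.5 mm | 98% | 75% | 51% |

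The nominal rate is 5%. This is the pre-post contrast of the 3x3 model. Using the pooled within-arm error (27 df) changes the result for 0.9 mm and SD 3 mm only from 35.6% to 35.4%.

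**4. Shift common to all arms: group-by-time.** For two visits, the interaction test is a one-way ANOVA of the change scores. A common shift adds the same constant to every change, so the differences between arms do not move and the error rate stays at 5%.

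**5. Shift in the two supplement arms only (20 men), none in Ex only (10 men).** The mean shift is two thirds of the shift s. The between-arm sum of squares is 20(s/3)² + 10(2s/3)² = 6.667 s², which is 5.4 for 0.9 mm and 15.0 for 1.5 mm. Noncentrality λ is this divided by SD²; F has 2 and 27 df, critical value 3.354.

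| Summed shift | SD 2 mm | SD 3 mm | SD 4 mm |
|---|---|---|---|
| 0.9 mm | λ 1.35: 15% | λ 0.60: 9% | λ 0.34: 7% |
| 1.5 mm | λ 3.75: 36% | λ 1.67: 18% | λ 0.94: 12% |

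**6. Cross-check from the ICCs.** Taking measurement error as the only source of change, the SD of change in between-person SD units is √(2(1 − ICC)): 0.576 at 0.834 (the lowest confidence limit reported), 0.214 at 0.977 and 0.100 at 0.995. In simulation (20,000 runs per case, arms 9/11/10), a shift of 0.1 SD gave:

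| ICC | Common shift, time | Common shift, group-by-time | Supplement arms only, group-by-time |
|---|---|---|---|
| 0.834 | 15% | about 5% | 6% |
| 0.977 | 69% | about 5% | 16% |
| 0.995 | over 99% | about 5% | 58% |

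True variation in response lowers these rates. With an SD of change of 0.45 to 0.63, the common shift gives 22% to 14% on the time effect, still above 5%.

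**The case against.** The strongest reply is that Aim 1 concerns protein timing, which is tested by group-by-time, and a drift common to all arms cancels there. That is correct. A reader might infer that the timing comparison is compromised; steps 1 and 4 show that common drift leaves it at 5% and that Post-ex versus Pre-sleep is described as double-blind. A reader might also infer that there is no masking to arm at all. Section 3.5 contradicts that; the gap in arm masking is Ex only.

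The magnitudes rest on an assumed SD and shift. They also require the same direction at all three sites and no true change after 12 weeks of supervised training. That stands: they show what a shift of this size would do, not that one occurred.

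It is tempting to read section 3.7.2 as saying that the scanner also made the measurements. The text names one person for the scans and does not name the reader. A single operator is also a strength, because it removes between-operator variation.

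Finally, blind re-reading would not prevent every visit-related bias. Probe pressure is set during scanning, and the sites are located again at each visit. Coded images carry both forward. This limits the remedy but does not remove the case for it.

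**Conclusion.** The concern holds for the time effect on muscle thickness and for contrasts of Ex only with the supplement arms. No masking to visit or to Ex only membership is described, the product blinding cannot supply it, and section 3.8 tests and follows up the time effect without an untrained arm. Under the stated assumptions, a common shift of 0.9 to 1.5 mm in the sum raises the false-positive rate for time from 5% to about 36 to 75% at an SD of 3 mm (22 to 98% over SDs of 2 to 4 mm). Group-by-time is affected only if the shift differs by arm: about 7 to 36% over the same range when it is confined to the supplement arms. The documents do not show that any drift happened, and they give no ground for doubting Post-ex versus Pre-sleep on this account. This is an inexpensive improvement to one Aim 1 outcome, not a flaw in the main comparison.

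**What to change.** Save every image. Once a participant has finished, have the assistant who already works apart from outcome measurement (section 3.5) code the images. The same reader then measures them in random order without visit or arm labels, and only those values are analysed. Record the site distances at pre and reuse them at mid and post, because the skin marks wash off. The first step reduces border-placement bias and the second reduces site-location bias; probe-pressure bias remains.

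The text is in the past tense and does not say whether images were kept. If they were, blind re-reading is still possible. If not, state who read them and with what masking, and interpret the time effect and the Ex only contrasts with caution.

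Cost: a few hours to code and re-read about 90 image sets (30 men × 3 visits), and no values on the day of the scan. With stored images, no new scan, visit or reader is needed.

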3.7.3 Functional Capacity Assessments

3.7.3.1 Maximum Strength

Participants underwent 1-RM testing at pre-, mid-, and post-intervention for the leg press and chest press exercises. At the pre-intervention assessment, there was a 1-RM familiarization session approximately 5-7 days before retesting 1-RM to account for any potential learning effect. The highest pre-intervention 1-RM value obtained was considered baseline maximum strength. Prior to 1-RM testing, participants completed 5 minutes of light cycling on a stationary cycle (Monark 828E, Langley, WA) followed by a full body dynamic warm up that consisted of various body weight movements lasting approximately 5 minutes. Thereafter, leg press 1-RM procedures began with a specific warm-up consisting of a loaded leg press for 10 repetitions at 30%, 5 repetitions at 50%, 2 repetitions at 75%, and 1 repetition at 85% of estimated 1-RM. All warm-up sets were completed with 1-minute rest periods. Then 1-RM attempts began, which generally consisted of a 1st attempt at 95%, 2nd attempt at 97.5%, and 3rd attempt at 100% of estimated 1-RM with 3-minute rest periods between each attempt. The 1-RM attempt procedure continued until the participants could no longer complete a full repetition with the correct form. After a leg press 1-RM was established, the same procedures were followed for the chest press exercise.

To ensure consistency among participants, strict adherence to procedural instructions for the leg press and chest press exercises was required for each 1-RM attempt. For the leg press, participants began the exercise in a seated position with their feet approximately shoulder width apart on the platform and their legs and hips flexed to position the inguinal crease just below the top of the knee. At the start of each repetition, a verbal command (e.g. start, go) was given from the researcher to begin the attempt. Then the participants moved the platform by extending their

hips, knees, and ankles until their legs reached full extension. Thereafter, they returned to the starting position in a controlled manner by flexing their hips, knees and ankle. Additionally, participants were required to keep their back and buttocks in contact with the seat throughout the movement.

For the chest press, participants began in a seated position, feet flat on the ground, with their arms abducted to approximately 45-75° and flexed until their hand is aligned with their chest, while grabbing the machine handles. At the start of each repetition, a verbal command (e.g. start, go) was given from the researcher to begin the attempt. Then participants extended their arms completely and return the handles to the starting position in a controlled manner by flexing their arms. Throughout the exercise, participants were required to keep their head, back, buttocks, and thighs in contact with the seat, along with feet flat on the ground.

3.7.3.2 Muscular Power

Power was assessed during several sit to stand tasks by affixing a Tendo unit (TENDO Sports Machines, Trencin, Slovak Republic) cord to the participants; waist (133). For this assessment, participants began seated in a standard height chair (0.47 m) with their feet on the floor, arms crossed over their chest, and hands on the contralateral shoulder. Upon a verbal command, participants were instructed to stand from a seated position as fast as possible for 3 trials separated by 60 seconds of rest. The highest peak and average power of the 3 trials were recorded and used for analysis of muscle power.

The Tendo unit consists of 2 components, a velocity sensor and display unit. The velocity sensory has a cord with a velcro sleeve that was positioned perpendicular to the floor and attached to the right side of the participants' waist during each trial. As the participants stood, the

Tendo unit cord was pulled and the display unit calculated the average and peak power output from velocity (m/s) and body mass (kg) through the sit-to-stand motion.

3.7.3.3 Short Physical Performance Battery

The SPPB is a simple, common protocol for measuring physical performance in older adults, and therefore, was used to evaluate functional ability. The SPPB consists of 3 components performed in the following order: 1) balance, 2) gait speed, and 3) 5-chair stands. The balance test required participants to maintain their balance for up to 10 seconds for one trial with their feet in 3 different positions in the order of: side-by-side, semi tandem, and full tandem position. Participants were allowed to move their arms and bend knees during the trials but were not permitted to move their feet. Each position was verbally explained and visually demonstrated prior to the test. Balance time for each trial was recorded and used for scoring. If the participants were not able to complete any balance position for 10 seconds, the balance test was ended and the SPPB was continued with the next test. For the gait speed test, participants were instructed to walk a 4-meter course at a normal pace for 2 trials, with the best time used for scoring. The 4-meter course was marked off by two pieces of tape on the floor. Participants started with both feet behind the tape and walked at a normal pace for 4-meters until they completely crossed the 2nd piece of tape. The last SPPB test was the 5-chair stands, which involved completing 5 consecutive sit-to-stand tasks as quickly as possible. Participants began in a seated position in a standard height chair (0.47 m) with their feet on the floor, arms crossed over their chest, and hands on the contralateral shoulder. Following a verbal command, they stood as quickly as possible and returned to a seated position. The test was finished upon the 5th standing motion, or if the participants could not complete 5 chair stands.

Interpretation of the SPPB outcomes was in accordance with previously established values (140). Briefly, each SPPB test was scored on a 0-4 scale, based upon time or completion of the task, with lower values indicating worse performance and vice versa. Scoring for the balance portion of the SPPB will consisted of: 1 point for maintaining the side-by-side position for 10 seconds, 1 point for maintaining the semi-tandem for 10 seconds, and 1 point for maintaining the full-tandem position between 3–9.99 seconds or 2 points for maintaining the full-tandem position for 10 seconds. If the participant could not maintain the side-by-side position for 10 seconds, the balance portion was scored 0. The gait speed test scoring was based upon the amount of time to walk 4 meters at a normal pace using the following cut off times: 1 point for times greater than 8.70 seconds, 2 points for times between 6.21–8.69 seconds, 3 points for times between 4.82–6.20 seconds, and 4 points for times less than 4.82 seconds. If the participants could not complete the 4-meter walk, then the gait speed test was scored as 0. Lastly, the 5-chair stand scoring was also based upon cut off times including: 1 point for times greater than 16.70 seconds, 2 points for times between 13.70–16.69 seconds, 3 points for times between 11.20–13.69 seconds, and 4 points for times less than 11.19 seconds. If the participant could not complete a sit-to-stand task, then the 5-chair stand test was scored as 0. Once all portions of the SPPB were completed the scores from all 3 tests were summed together for a total score, with 12 being the highest possible score.

3.7.4 Cognitive Processing Speed

3.7.4.1 Digit Symbol Substitution Task

The digit symbol substitution (DSST) task is a well-validated psychomotor test used to assess processing speed (304). Participants were provided a series of digits (1-9) with a corresponding symbol beneath each digit, which together represents a “key” for the task. Below

this “key” was a series of digits in random order with an empty box underneath each digit. The task of the participants was to copy the associated symbol in the empty box beneath each digit, in order, as quickly as possible. This task was then scored based upon the number of symbols copied correctly within 90 seconds. A pencil and paper version of this test was used.

3.7.4.2 Pattern Comparison

The pattern comparison task is a simple 2-page, 60-second test (30-seconds per page) that assesses processing speed by requiring participants to visually examine several pairs of side-by-side images to determine if they are the same or different (58). The pencil and paper version of this test was used, which requires participants to write “S” or “D” (for “same” or “different”) depending on whether they believed the images were identical or not. The score was the correct number of judgments within 60 seconds.

3.7.5 Psychological Assessments

3.7.5.1 Appetite

A visual analog scale (VAS) was used to assess changes in appetite. The VAS is 100-mm horizontal scale with opposite extremes that represent three appetite sensations (hunger, satiety, and desire to eat) positioned at each end of the 100-mm line (0 = “not at all” and 100 = “extremely”). Following an overnight fast during the pre- and post-testing points, participants were asked to rate their subjective feelings, at that moment, by placing a vertical line along the 100-mm scale. These ratings were converted to a score in millimeters using a standard millimeter ruler. Higher scores indicated greater feelings of each sensation.

